9.0 DRUG INFORMATION

9.1 TMZ

Study sites must refer to the TMZ package insert for detailed pharmacologic and safety information.

See Section 5.3 for TMZ administration instructions. Refer to the current package insert/SmPC provided with each drug and the site-specific pharmacy for toxicity information and instructions for drug preparation, handling, and storage.

9.1.1 TMZ Supply

TMZ is commercially available.

9.2 ABT-414

9.2.1 Identification of Investigational Product(s)

Information about ABT-414 formulations to be used in this study is presented in [Table 13](#).

Table 13. Identification of Investigational Product(s)

Study Drug	Formulation	Dosage Form	Strength (mg)	Manufacturer
ABT-414	Sucrose, histidine, polysorbate 80	Sterile lyophilisate in a vial (to be reconstituted and further diluted for IV infusion)	100 mg 20 mg	AbbVie
Placebo for ABT-414	Sucrose, histidine, polysorbate 80	Sterile lyophilisate in a vial (to be reconstituted and further diluted for IV infusion)	100 mg 20 mg	AbbVie

9.2.2 Packaging and Labeling of Blinded ABT-414/Placebo

Vials containing ABT-414 lyophilized powder or placebo will be packaged in cartons in a blinded fashion. Vials containing ABT-414 lyophilized powder designated for the hepatic impairment sub-study will be packaged in cartons in an open-labeled fashion. Each vial and carton will be labeled per country requirements.

9.2.3 Storage and Disposition of ABT-414/Placebo

The ABT-414 and placebo lyophilisate for injection must be stored refrigerated at 2°C to 8°C/36°F to 46°F, protected from light, and must not be frozen.

The reconstituted ABT-414 or Placebo should be refrigerated at 2°C to 8°C/36°F to 46°F, for no more than 20 hours. After storage at 2°C to 8°C/36°F to 46°F, the solution can be allowed to come to room temperature and be administered within 4 hours. From start to reconstitution until the infusion is completed, a total of 24 hours should not be exceeded. If maintained at room temperature, the solution should be used within 4 hours.

Storage temperature logs will be maintained to document proper storage conditions. The refrigerator temperature must be recorded on a daily basis on the temperature logs to record proper function. Temperature excursions must be reported to AbbVie immediately.

The investigational products are for investigational use only and are to be used only within the context of this study. The study drug supplied for this study must be maintained under adequate security and stored under the conditions specified on the label until dispensed for subject use or returned to AbbVie.

9.2.4 Preparation/Reconstitution of Dosage Form

ABT-414/placebo Study Medication Preparation Guidelines will be provided as a separate document outside of this protocol.

9.2.5 Product Complaint

9.2.5.1 Definition

A Product Complaint is any Complaint related to the biologic or drug component of the product.

For a product this may include, but is not limited to, damaged/broken product or packaging, product appearance whose color/markings do not match the labeling, labeling discrepancies/inadequacies in the labeling/instructions (example: printing illegible), missing components/product, or packaging issues.

Any information available to help in the determination of causality to the events outlined directly above should be captured.

9.2.5.2 Reporting

Product Complaints concerning the investigational product must be reported to the Sponsor within 24 hours of the study site's knowledge of the event via the Product Complaint form. Product Complaints occurring during the study will be followed-up to a satisfactory conclusion. All follow-up information is to be reported to the Sponsor (or an authorized representative) and documented in source as required by the Sponsor. Product Complaints associated with adverse events will be reported in the study summary. All other complaints will be monitored on an ongoing basis.

Product Complaints may require return of the product with the alleged complaint condition. In instances where a return is requested, every effort should be made by the Investigator to return the product within 30 days. If returns cannot be accommodated within 30 days, the site will need to provide justification and an estimated date of return.

The description of the complaint is important for AbbVie in order to enable AbbVie to investigate and determine if any corrective actions are required.

10.0

PATHOLOGY/BIOSPECIMENS

Tumor tissue for *EGFR* assessment should be prepared and sent to central lab as described in the study specific laboratory manual and outlined in Section [4.2](#).

11.0 DATA AND RECORDS

11.1 Source Documents

Source documents are defined as original documents, data and records. These may include hospital records, clinical and office charts, laboratory data/information, subject diaries or evaluation checklists, pharmacy dispensing and other records, recorded data from automated instruments, microfiches, photographic negatives, microfilm or magnetic media, and/or x-rays. Source document data may be transcribed onto electronic case report forms (eCRFs) as required. Data collected during this study must be recorded on the appropriate source document.

For all adverse events, the onset date and event description will be captured in source documents. Other adverse event data points required for eCRF completion can be entered directly in the eCRF and may serve as the source document and should be printed, signed and dated by the Investigator.

The Investigator/institution will permit study-related monitoring, audits, IEC/IRB review, and regulatory inspection(s), providing direct access to source data documents.

11.2 Case Report Forms

Case report forms (CRF) must be completed for each subject screened/enrolled in this study. These forms will be used to transmit information collected during the study to AbbVie and regulatory authorities, as applicable. The CRF data for this study are being collected with an electronic data capture (EDC) system called Rave[®] provided by the technology vendor Medidata Solutions Incorporated, NY, USA. The EDC system and the study-specific electronic case report forms (eCRFs) will comply with Title 21 CFR Part 11. The documentation related to the validation of the EDC system is available through the vendor, Medidata, while the validation of the study-specific eCRFs will be conducted by AbbVie and will be maintained in the Trial Master File at AbbVie.

The Investigator will document subject data in his/her own subject files. These subject files will serve as source data for the study. All eCRF data required by this protocol will be recorded by investigative site personnel in the EDC system with the exception of the ePRO information which will be integrated into the eCRFs electronically. All data entered into the eCRF will be supported by source documentation.

The Investigator or an authorized member of the Investigator's staff will make any necessary corrections to the eCRF. All change information, including the date and person performing the

corrections, will be available via the audit trail, which is part of the EDC system. For any correction, a reason for the alteration will be provided. The eCRFs will be reviewed periodically for completeness, legibility, and acceptability by AbbVie personnel (or their representatives). AbbVie (or their representatives) will also be allowed access to all source documents pertinent to the study in order to verify eCRF entries. The principal Investigator will review the eCRFs for completeness and accuracy and provide his or her electronic signature and date to eCRFs as evidence thereof.

Medidata will provide access to the EDC system for the duration of the trial through a password-protected method of internet access. Such access will be removed from Investigator sites at the end of the site's participation in the study. Data from the EDC system will be archived on appropriate data media (CD-ROM, etc.) and provided to the Investigator at that time as a durable record of the site's eCRF data. It will be possible for the Investigator to make paper printouts from that media.

14.1 Study Design

This is a Phase 3 study. The primary objective of the study is to assess whether ABT-414 in combination with concomitant TMZ/RT followed by combination of ABT-414 with adjuvant TMZ improves *overall survival* (OS) compared to concomitant TMZ/RT + adjuvant TMZ in subjects with EGFR-amplified GBM. A total of 640 evaluable subjects will be randomized.

14.2 Statistical Methods

This is a comparative randomized, placebo controlled, double-blinded Phase 3 trial. All efficacy analyses will be performed in the Full Analysis Set (defined below). OS (primary efficacy endpoint for the overall study) and PFS (secondary efficacy endpoint) will be compared between treatment Arms A and B using stratified log-rank test statistics or a weighted version of this test (to be pre-specified in the Statistical Analysis Plan document (the SAP)), adjusting for the study stratification factors. PFS is defined as time from randomization to progression of disease (per RANO criteria) or death, whichever occurs first.

Randomization and Stratification

MGMT methylation status and RPA (referenced in [Appendix VI](#)) are demonstrated to be prognostic of survival for newly diagnosed GBM subjects. For this study, subjects will be stratified by *MGMT* methylation status (methylated versus unmethylated), RPA class (III versus IV versus V), region of the world (US/Canada versus other) and *EGFRvIII* mutation status (mutated versus other), where *EGFRvIII* other is defined as wild type, indeterminate due to test failure, invalid, or insufficient tissue. *EGFRvIII* is a stratification factor because it is potentially prognostic and because it is related to the mechanism of action of ABT-414 which binds to both activated wild type *EGFR* and *EGFRvIII*. After stratification, subjects will be randomized to either Arm A or Arm B in a 1:1 ratio.

Analysis Sets

The following analysis sets will be used for analysis of safety and primary and secondary efficacy endpoints of the study:

- Full Analysis Set (FAS) will comprise all randomized subjects regardless of whether they received study treatment. Subjects will be classified according to the treatment they were assigned at the time of randomization. The FAS will be the primary analysis set for the analysis of efficacy endpoints.

- Safety Analysis Set (SAS) will comprise all randomized subjects who receive at least one dose of study treatment (either RT, TMZ or ABT-414). Subjects will be classified according to treatment received. Thus a subject randomized to Arm A who receives RT+TMZ but does not receive ABT-414 will be considered in the control group (Arm B) for safety analysis.
- Per-protocol Set (PPS) will comprise all randomized subjects excluding those with major deviation from study inclusion and exclusion criteria, compliance with procedures. Subjects will be classified according to treatment assigned. The PPS will be used for supportive analysis of efficacy endpoints.

14.3 Primary Endpoints Study Design

14.3.1 Primary Endpoint

The primary endpoint for this study is OS, defined as time from randomization to death from any cause. For subjects who are not reported to have died at the time of an analysis, OS will be right-censored at the last date the subject is documented to be alive.

14.3.2 How Primary Endpoint Will Be Analyzed

Efficacy analysis for the overall study will be performed in the FAS which includes all randomized subjects regardless of whether or not they received study treatment. The PPS will be used for supportive analysis of efficacy endpoints. The primary endpoint for the overall study is overall survival (OS). To meet the primary objective, OS will be compared between treatment Arms A and B for the FAS and PPS using stratified log-rank test statistics or a weighted version of the test, adjusting for the study stratification factors and additional independent prognostic factors as deemed appropriate, to be specified in the SAP. If a weighted version is considered to be more appropriate in view of potentially delayed treatment effect, it will be pre-specified in the SAP prior to conducting any unblinded analysis of study data. The hazard-ratio of OS for ABT-414 Arm A compared to placebo Arm B will be estimated by fitting Cox-proportional hazards regression models adjusting for the main-effects of the stratification factors and additional independent prognostic factors as deemed appropriate, to be specified in the SAP.

Type I Error Control

To maintain overall type I error control for the overall study, each secondary endpoint will be tested in the order listed if the primary endpoint (OS) and all preceding secondary endpoints show statistically significant results at the one-sided 0.025 level of significance.

The O'Brien-Fleming method will be implemented to protect the one-sided type I error of 0.025. Specifically, a nominal alpha level of 0.00965 will be used for the interim efficacy analysis for OS. For the final analysis, the primary efficacy endpoint will be tested at the one-sided nominal alpha level of 0.0221 after adjusting for the interim looks at efficacy data.

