An interim superiority and futility analysis of efficacy data will be performed when 75% (332) of the 441 required maximum number of deaths are observed. The analysis will be performed using the Full Analysis Set, with all randomized cases being included in the treatment arm to which they were randomized regardless of what treatment the subjects actually received. The primary endpoint of OS will be compared between treatment Arms A and B using stratified log-rank test statistics (or, a weighted version, as pre-specified in the SAP) adjusting for the study stratification factors and additional independent prognostic factors as deemed appropriate, to be specified in the SAP. The hazard-ratio of OS for ABT-414 Arm A compared to placebo Arm B will be estimated by fitting Cox-proportional hazards regression models adjusting for the main-effects of the stratification factors and additional independent prognostic factors as deemed appropriate, to be specified in the SAP. Adjustment of the level of significance (alpha) for multiple testing will be made using the O'Brien-Fleming group sequential spending function for early rejection of the null hypothesis to declare superiority. Superiority will therefore be assessed at a one-sided significance level of 0.00965, which is corresponding to a Z-score superiority boundary at -2.34 . The trial may also be stopped for futility following this interim analysis if the estimated Cox hazard ratio of ABT-414 Arm A to placebo Arm B at interim analysis exceeds 0.9.

The unblinded interim results will first be reviewed by the IDMC, and the trial will be considered for early stopping if the IDMC makes such a recommendation after consideration of the OS results and all supportive evidence including all secondary endpoints and safety. For the final analysis, the primary efficacy endpoint will be tested at the one-sided nominal alpha level of 0.0221 after adjusting for the interim looks at efficacy data. Details for the interim efficacy analysis will be provided in the IDMC charter.

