To maintain overall type I error control for the overall study, each secondary endpoint will be tested in the order listed if the primary endpoint (OS) and all preceding secondary endpoints show statistically significant results at the 1-sided 0.025 level of significance. The O'Brien-Fleming method will be implemented to protect the one-sided type I error of 0.025. A nominal alpha level of 0.00969 will be used for the interim efficacy analysis for OS. For the final analysis, the primary efficacy endpoint will be tested at the one-sided nominal alpha level of 0.0221 after adjusting for the interim look at efficacy data.

Pharmacokinetic:

Peak and trough concentrations (C_{max} and C_{trough}) of ABT-414 and total ABT-806 antibody will be summarized from the observed concentration data. Population pharmacokinetic parameters of ABT-414, total ABT-806 and cys-mcMMAF such as clearance and volume of distribution will be estimated using a nonlinear mixed effect modeling analysis.

Safety Analysis:

AbbVie will assess adverse events, laboratory data, and vital signs throughout the study. Analyses of adverse events will include only "treatment-emergent" events, i.e., those that start or worsen on or after the day of the first dose of study drug. Adverse events severity and laboratory evaluation changes will be assessed by utilizing National Cancer Institute (NCI) Common Terminology Criteria for Adverse Events (CTCAE) Version 4.0. Adverse events will be summarized by preferred terms within a System and Organ Class according to the most current Medical Dictionary for Regulatory Activities (MedDRA) dictionary. Changes from baseline will be analyzed for each scheduled post-baseline visit and for the final visit for blood chemistry and hematology parameters, as well as urinalysis and vital sign parameters. Shifts in laboratory values from baseline NCI CTCAE grades to maximum and final post-baseline grades will be assessed.

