5.6 Multiplicity Testing Procedures for Type-I Error Control

5.6.1 Type I error control for interim analysis

O'Brien-Fleming method will be used to adjust for multiple testing to maintain overall one-sided type I error level at 2.5%. As described in Section 10.2, Fleming-Harrington version of weighted log-rank test^{10,12} would be used for primary efficacy analyses with weights for the events occurring at time t as

$$w(t) = [1 - \hat{S}_{KM}(t)]^{0.2}$$

where, $\hat{S}_{KM}(\cdot)$ is the KM estimate of the survival function in the pooled data.

The weight for d^{th} event occurring at time t_d can be calculated as

$$w_d \equiv w(t_d) = [1 - \hat{S}_{KM}(t_d)]^{0.2} ,$$

and the information fraction (IF) can be estimated as (Hasegawa, 2016)

$$IF = \left(\sum_{d=1}^{D_{IA}} w_d^2 \right) / \left(\sum_{d=1}^{D_{FA}} w_d^2 \right)$$

where D_{IA} and D_{FA} denote the planned number of events at the interim and final analysis, respectively. With interim analysis planned at 332 events and final analysis planned at 441 events, the simulation results suggest that the IF at the interim analysis is estimated to be approximately 66%. With this IF at interim analyses, a one-sided type I error of 0.0058 will be used for interim analysis with 332 events for early efficacy, and final analysis will be carried out at one-sided type I error of 0.0232 to preserve overall type I error at one sided 2.5%.

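### The protocol and the SAP set different OS efficacy boundaries, and the protocol's pair spends slightly more than 2.5% on the weighted test the trial uses

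*Protocol*

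**What the plan says.** Protocol 14.3.2 names the method and the target: "The O'Brien-Fleming method will be implemented to protect the one-sided type I error of 0.025". It then fixes two nominal one-sided levels. At the interim, "a nominal alpha level of 0.00965 will be used for the interim efficacy analysis for OS"; at the final analysis, "the primary efficacy endpoint will be tested at the one-sided nominal alpha level of 0.0221". Protocol 14.4 repeats both, ties the interim level to a Z boundary of -2.34, and describes the adjustment as "using the O'Brien-Fleming group sequential spending function for early rejection of the null hypothesis to declare superiority". The synopsis (Appendix II, Type I Error Control) keeps 0.0221 but gives a different interim figure: "A nominal alpha level of 0.00969 will be used for the interim efficacy analysis for OS".

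The protocol allows either a stratified log-rank test or a weighted version to be named in the SAP. SAP 10.2 makes that choice: a stratified Fleming-Harrington weighted log-rank test with rho = 0 and gamma = 0.2. SAP 5.5.1 and 5.6.1 estimate its information fraction at 332 deaths as about 66%, and SAP 5.6.1 sets the levels accordingly: "a one-sided type I error of 0.0058 will be used for interim analysis with 332 events for early efficacy". The same section puts the level for the last look at 0.0232.

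**The concern.** One primary test at one planned interim has three printed efficacy levels (0.00965, 0.00969 and 0.0058), and the final analysis has two (0.0221 and 0.0232). The protocol hands the choice of test to the SAP. It states its levels as plain numbers and does not say that they change with the test or that the SAP overrides them.

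Three things are at stake. The documents can give opposite verdicts on the same p-value, at the interim and at the final analysis. The protocol's levels may not hold 2.5% for the chosen test. And because OS is the gate for every secondary endpoint (protocol 14.3.2, SAP 5.6.2), any doubt about the OS verdict passes down the whole hierarchy.

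**Working it through.** **Inputs.** Overall one-sided error 0.025 (protocol 14.3.2, SAP 5.6.1). Interim and final deaths 332 and 441 (protocol 14.4, SAP 5.5.1). Weighted information fraction about 0.66 (SAP 5.5.1, 5.6.1). Design hazard ratio 0.75 (protocol 14.3.3, SAP 5.4).

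**Step 1: reproduce the printed levels.** With O'Brien-Fleming-type (Lan-DeMets) spending, the interim level at information fraction t is 2[1 − Φ(z(0.9875)/√t)]. The final level is solved from a bivariate normal with correlation √t so that the total is 0.025.

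| t | Interim level | Interim Z | Final level |
|---|---|---|---|
| 0.75 | 0.00965 | 2.340 | 0.0221 |
| 332/441 = 0.7528 | 0.00979 | 2.334 | 0.0221 |
| 0.66 | 0.00580 | 2.524 | 0.0232 |

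The protocol's pair reproduces at t = 0.75, the fraction for an unweighted log-rank test. The SAP's pair reproduces at t = 0.66. The synopsis value 0.00969 appears at neither 0.75 nor 332/441, and the classic O'Brien-Fleming boundary at 0.75 gives 0.00998.

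**Step 2: total error of each pair on the weighted test.** The total is P(Z1 > z(a1) or Z2 > z(a2)) under the null, with correlation √t.

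| t | Protocol pair (0.00965, 0.0221) | SAP pair (0.0058, 0.0232) |
|---|---|---|
| 0.65 | 0.0261 | 0.0251 |
| 0.66 | 0.0260 | 0.0250 |
| 0.70 | 0.0256 | 0.0247 |
| 0.75 | 0.0250 | 0.0244 |

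Keeping 0.00965 at t = 0.66 would require a final level of about 0.0210, not 0.0221.

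**Step 3: check the 66%.** A simulation of the Fleming-Harrington (0, 0.2) test used 12,000 trials. It assumed exponential survival, a control median of 16 months, 640 patients and uniform accrual over 29 months. It gave an information fraction of about 0.69, where the protocol pair spends about 0.0257. The simulated rejection rate for that pair was 0.0250, with a Monte Carlo standard error of √(0.025 × 0.975/12,000) = 0.0014. That is too coarse to show an excess of this size, so the excess rests on the bivariate normal calculation.

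**Step 4: size of the conflict at the interim** (unweighted approximation).
- Hazard-ratio boundary, exp(−2z/√332). Protocol: exp(−2 × 2.340/18.22) = 0.774. SAP: exp(−2 × 2.524/18.22) = 0.758.
- Mean interim Z at hazard ratio 0.75: |ln 0.75| × √332/2 = 0.2877 × 18.22/2 = 2.62.
- P(2.340 < Z < 2.524) = Φ(−0.10) − Φ(−0.28) = 0.072.
- Under the null, the same zone has probability 0.00965 − 0.0058 = 0.00385.

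**Step 5: power.** With 441 deaths at hazard ratio 0.75, group-sequential power is 84.9% with the protocol pair at t = 0.75 and 85.1% with the SAP pair at t = 0.66. The stated 85% holds either way.

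**The case against.** The protocol's figures are not miscalculated; they are right for a different test. No document tells anyone to run the protocol's levels on the weighted test, because the SAP that names the test also gives its levels. Both documents share the same spending method and the same 2.5%. The error excess is therefore hypothetical, and at most about 0.1 percentage point. The synopsis figure differs from the body by 0.00004 and looks like a slip. The 7% figure applies only at a hazard ratio of exactly 0.75. The reported interim (346 deaths, weighted one-sided p = 0.628, hazard ratio 1.01) was far from every boundary, and the protocol says that no more efficacy data will be collected.

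All of that stands as a statement of scale. It does not remove the conflict. The protocol delegates the test but not the levels, and it sends interim detail to the IDMC charter, not to the SAP.

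Dates do not settle precedence either. The SAP is dated 23 April 2019 and was written to protocol Amendment 8 of 29 November 2018. The protocol synopsis is dated 26 May 2019. That later date appears to come from an amendment reporting the interim result: the part of its change list available here shows no edit to the statistical sections. So it is not evidence of a fresh boundary decision. Still, the most recent protocol text carries the unweighted levels.

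**Conclusion.** The concern holds: the protocol's OS boundaries are wrong as written for the test that the trial uses. The SAP pair is the correct one at an information fraction of 0.66, and is slightly conservative if the fraction is higher.

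The type I error excess is small: 0.0260 at t = 0.66 and about 0.0257 at 0.69, against 0.025. It assumes joint normality of the two statistics and that the protocol pair is applied to the weighted test. The conflict between thresholds matters more. An interim p-value from 0.0058 to 0.00965, or a final one from 0.0221 to 0.0232, gets opposite verdicts. The interim zone has about a 7% chance at hazard ratio 0.75, assuming proportional hazards and an unweighted Z.

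The reported interim decision is unaffected. The defect is that the primary decision rule was not unique before unblinding.

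**What to change.** In protocol 14.3.2, 14.4 and the synopsis, replace 0.00965, 0.00969, Z = -2.34 and 0.0221 with the levels for the Fleming-Harrington test: 0.0058 (Z about -2.52) at the interim and 0.0232 (Z about -1.99) at the final analysis. Add that both are recalculated with the same spending function from the weighted information fraction actually observed. The interim was in fact run at 346 deaths, not 332, so any level printed for exactly 332 is only approximate. A sentence stating that the SAP governs the nominal levels for the selected test would also remove the contradiction, provided the protocol's fixed numbers are deleted.

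The cost is wording in three places. The interim boundary becomes stricter, the final one slightly looser, and power stays at about 85%. Sample size and data collection do not change.
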